4.7 Data Safety Monitoring Committee

A Data and Safety Monitoring Board (DSMB) will be used to evaluate safety as needed during the trial and to review results of interim efficacy and safety analyses. The DSMB will consist of at least two clinicians (who are not Investigators for this trial) and one biostatistician with expertise in oncology trials. The DSMB will make recommendations to the Sponsor regarding the conduct of the study, including possible early discontinuation of the study for excessive toxicity or extreme efficacy. A separate DSMB Charter document will specify the procedures governing the conduct of the DSMB. Qualified individuals not affiliated with the Sponsor, including a statistician, will be responsible for preparing reports for the DSMB.

4.8 Duration of Treatment and Follow-Up

Considering the estimated accrual rate of 4-6 subjects per month, the total duration of the study after the first visit of the first subject is about 36 months.

At the time of study closing, the duration will be approximately 34 months.

5. Study Treatments

5.1 Method of Assigning Subjects to Treatment Groups

All enrolled subjects will receive the same course of study drug(s) in the respective Treatment Periods. Following providing informed consent, potential subjects will be assigned a subject identification number and undergo screening procedures to determine eligibility for the study.

Subjects satisfying all inclusion/exclusion criteria who are PrR positive will be enrolled in Treatment Period 1 and receive MA only. MA will be taken p.o. in a total daily dose of 160 mg. MA is a synthetic derivative of the naturally occurring steroid hormone progesterone and is Food and Drug Administration (FDA) approved for the treatment of advanced endometrial cancer.

Subjects determined to be PrR negative at Screening will not enroll in Treatment Period 1. These subjects will enroll directly into Treatment Period 2. All subjects who achieve disease control (CR, PR, or SD) as indicated by tumor assessment after Treatment Period 1, will be ineligible to enter Treatment Period 2. Additionally, subjects who discontinue Treatment Period 1 prematurely (receiving < 4 weeks of progestin monotherapy) for any reason will also be excluded from the remainder of the study. All other subjects may enroll in Treatment Period 2. During Treatment Period 2, subjects will receive MA in combination with Sodium Cridanimod. Sodium Cridanimod is a synthetic interferon inducer that was developed for use against viral infections. Sodium Cridanimod has been shown to increase endometrial cancer expression of PrR and increase the efficacy of progestin therapy in some hormone resistant recurrent or persistent endometrial cancer subjects. During Treatment Period 2:

- MA is to be taken p.o. in a total daily dose of 160 mg. Subjects will be provided a diary and instructed to record all doses of MA. At Study Visits when both SC and MA are to be administered, the dose of MA should be administered prior to SC. Whenever possible, the a.m. or p.m. dose of megestrol acetate should be taken in the clinic during the Study Visit.
- SC (500 mg / 4 mL) is to be diluted with 1 mL of 2% lidocaine hydrochloride (5 mL total) and administered twice a week i.m. in accordance with either Schedule 1 (Mondays and Thursdays) or Schedule 2 (Tuesdays and Fridays). For SC doses that do not correspond to a Study Visit, the drug may be administered either at the clinical site or at home by a medical service provider.

5.2 Blinding and Unblinding

This is an open-label, single-arm study; therefore, no randomization or blinding procedures will be performed.

5.3 Dose Modifications

There will be no allowed modifications to the dosage, including dose reduction, of either MA or SC during the trial.

If an injection of SC is not administered on the scheduled dosing date, this can be done during the next two days but no later than 1 day before the next scheduled dose. The subsequent injection of SC should be given in accordance with the study drug administration schedule. If a subject misses a dose of MA, the next dose should be taken at the regularly scheduled time.

SC and MA combination therapy should be discontinued if an AE of Grade 3 or higher (in accordance with NCI-CTCAE [National Cancer Institute-Common Terminology Criteria for Adverse Events] Version 4.03 criteria) is observed and determined to be potentially related to either medication. When combination treatment is discontinued, both SC and MA are to be discontinued. Monotherapy in Treatment Period 2 is not permitted. The treatment will not be re-started and the subject will be withdrawn from Treatment Period 2 and enter the Follow-Up Period.

6. Sample Size and Power Considerations

The primary objective of the study is to evaluate the efficacy of the study drug by the frequency of subjects with overall disease control (CR, PR and SD). The null hypothesis assumes an historical disease control rate of < 5%, given that these subjects have already failed progestin therapy. A clinically significant difference is predefined as a 15% increase (i.e. disease control rate of 20%). Using A'Hern's update of Fleming's single stage procedure (in which a predetermined number of subjects is recruited to the study and a decision about activity is obtained from the number of responses [including CR, PR] and SD amongst these subjects) with the probabilities of type I and type II errors of 5% (one-sided) and 10%, respectively, approximately 40 subjects are needed to contribute to the primary analysis in

Treatment Period 2. It is estimated that approximately 20-25% of all enrolled subjects will be classified as PrR negative and go directly into Treatment Period 2. This group will represent 14-16 of the Treatment Period 2 subjects. The rate of subjects who will have PD following treatment with MA in Treatment Period 1 and then move on to Treatment Period 2 is estimated at 55-60%. These subjects will represent 30-32 of the Treatment Period 2 subjects (estimating that approximately 24-25 subjects treated in Treatment Period 1 will not exhibit PD and will not move into Treatment Period 2.) Estimating the rate of subjects who will be unavailable for disease assessment for various reasons at 10-15%, it is planned to enroll 72 total subjects. An estimated 20% screen failure rate will require up to 90 screened subjects to allow for enrollment of 72 subjects.

Since the study is closing early, no summaries of overall disease control rate, or overall response rate will be calculated as part of the final analysis. Thus, the sample size calculations are no longer applicable.

7. Data Preparation

All reported study data will be recorded on the electronic Case Report Forms (eCRF) supplied by Statistics and Data Corporation, Inc. (SDC) using iMedNet, v1.164.1 or higher. Only the Principal Investigator and authorized study staff in accordance with the Delegation of Responsibilities log are entitled to make entries in the eCRF.

- After data are entered in the clinical study database, electronic edit checks and data review will be performed. All data validation specifications and procedures are detailed in the Data Validation Manual as a separate document. When the database has been declared to be complete and accurate, the database will be locked. Any changes to the database after data have been locked can only be made with the approval of the Sponsor in consultation with SDC.

All analyses outlined in this document will be carried out after the following have occurred:

- All data management requirements are met in accordance with SDC standard operating procedures, including data entry, performance of edit and validation checks, documentation and resolution of data queries, and database lock with written authorization provided by appropriate SDC and Sponsor personnel
- Protocol deviations have been identified and status defined (major/minor deviations)
- Analysis populations have been determined

8. Analysis Populations

All subjects who sign the informed consent, satisfy all eligibility requirements and are assigned a subject number (CCC-SS-XX), which consists of a 3-digit country code (CCC), a 2-digit site number (SS)

followed by 2-digit consecutive enrollment number (XX) will be considered enrolled subjects. This will be the population used in the disposition listings. Subjects who do not satisfy the criteria as enrolled subjects are considered screen failures. The following subsets of the enrolled subjects will be used for all other analyses.

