8.1 Safety Population

1. The Safety Population will consist of all subjects who receive at least one full or partial dose of either study treatment. For subjects treated solely in Treatment Period 1 this will include all subjects treated with at least one full or partial dose of MA. For all other subjects, the Safety Population will include all subjects treated with at least one full or partial dose of either MA or SC. Safety data will be reported separately for subjects in Treatment Period 1 who do not go on to Treatment Period 2, and for those subjects in Treatment Period 1 who are treated in both periods.

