9.2 Missing Data and Adjustments for Multiplicity

This is a phase 2, exploratory study. Missing values will not be estimated. All data will be included in safety analysis. Censoring rules for time to event analyses are described in Section 14. Since no

statistical testing will be performed, there will be no adjustments for multiplicity. Fleming's procedure is based on a one sample hypothesis test for a proportion. Because there is a single primary hypothesis, treatment corrections for multiplicity are not required.

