10.4 Protocol Deviations

Protocol deviations will be collected and monitored by the site monitors and transferred to SDC as an Excel spreadsheet. Protocol deviations are collected for the following categories:

- Assessment Not Done
- Assessment Out of Window
- Inclusion/Exclusion Criteria
- Safety Related
- Visit Not Done

Prior to database lock, deviations will be reviewed to determine major/minor status. Any violations of the inclusion or exclusion criteria or subject compliance in study drug administration outside of the 80-120% acceptable range will be considered major protocol deviations. A subject listing will be provided including the date of the deviation, the deviation category and description and the classification of whether the deviation was judged to be major or minor.

11. Demographic and Pretreatment Variables

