15.9.3 URINALYSIS

Urine samples are taken at the Screening Visit, at the End of Study Visit, at Visit 7, at Visit 13, every 12 weeks thereafter until disease progression and at the Safety Follow-Up Visit, and are analyzed at local laboratories.

Urine analysis will include:

- Blood
- Glucose
- Ketones
- pH
- Protein

The local laboratories will provide lab results, normal ranges and units to be entered on the eCRFs. All laboratory data will be converted to standard international units for reporting purposes.

Routine clinical laboratory evaluations (hematology, serum chemistry, and urinalysis) will be listed by subject with values outside of reference ranges marked. The high/low criteria will be determined based on the normal ranges provided by the laboratory.

16. Pharmacokinetic (PK) Analyses

No patients participated in the voluntary PK portion of the study therefore no PK data will be presented in the abbreviated analysis.

17. Pharmacodynamic Analyses

No Pharmacodynamic data will be collected for this study.

18. Quality of Life Analyses

No Quality of Life data will be collected for this study.

19. Interim Analyses

Since the study is closing early no interim analysis will be performed.

20. Changes from Protocol-Stated Analyses

Since the study is closing early, this SAP differs from the protocol-stated analysis in significant respects.

With the exception of one ECG table (summarizing QTc categories) all data will only be presented in listings. Two other particular differences are noted:

1. Protocol 7.2.1 states, "The Safety Population will consist of all subjects who receive at least one full or partial dose of study treatment (all treated subjects) in Treatment Period 2. This population will be used for all safety reporting." This SAP updates this to the following definition: The Safety Population will consist of all subjects who receive at least one full or partial dose of either study treatment. For subjects treated solely in Treatment Period 1 this will include all subjects treated with at least one full or partial dose of MA. For all other subjects, the Safety Population will include all subjects treated with at least one full or partial dose of either MA or SC. Safety data will be reported separately for subjects in Treatment Period 1 who do not go on to Treatment Period 2, and for those subjects in Treatment Period 1 who are treated in both periods.

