2. The primary efficacy endpoint ODCR and secondary efficacy endpoint ORR will not be assessed.
3. Protocol 7.7 indicates that protocol deviations will be collected on the eCRFs. Instead, deviations will be collected and monitored by the site monitors and transferred to SDC as an Excel spreadsheet.

Any changes to the planned analyses after database lock and unblinding will be described in the clinical study report.

21. References

R. P. A'Hern. Sample size tables for exact single-stage phase II designs. *Statist. Med.* 2001; 20:859:866.

Fleming TR. One sample multiple testing procedure for phase II clinical trials. *Biometrics* 1982; 38:143:151.

22. Revision History

Documentation of revision to the SAP will commence after approval of the Final version 1.0.

23. Tables

14.3.3.7	Electrocardiogram QTcB and QTcF Categories	Safety Population
----------	--	-------------------

24. Figures

14.2.1.1	Swimmer's Plot of Treatment and Response Durations	Safety Population Population – Subjects who Participated in Treatment Period 2
----------	--	---

25. Listings

Listing Number	Title	Population
16.2.1.1	Subject Disposition	All Enrolled Subjects
16.2.1.2	Screen Failures	All Screened Subjects
16.2.1.3	Informed Consent	All Enrolled Subjects
16.2.1.4	Visit Dates	All Enrolled Subjects
16.2.1.5	Inclusion and Exclusion	All Enrolled Subjects
16.2.2	Protocol Deviations	All Enrolled Subjects
16.2.3	Analysis and Treatment Period Populations	All Enrolled Subjects
16.2.4.1	Demographics and Baseline Characteristics	Safety Population
16.2.4.2	Baseline Disease Characteristics and PrR Status	Safety Population
16.2.4.3	Medical and Surgical History	Safety Population
16.2.4.4	Prior and Concomitant Medications	Safety Population
16.2.4.5.1	Prior Chemotherapy	Safety Population
16.2.4.5.2	Prior Hormonal Therapy	Safety Population
16.2.4.5.3	Prior Radiotherapy	Safety Population
16.2.4.5.4	Prior Cancer Surgery	Safety Population
16.2.4.6	Pregnancy Test Results	Safety Population
16.2.5.1	Sodium Cridanimod Administration	Safety Population

Listing Number	Title	Population
16.2.5.2	Megestrol Acetate Diary	Safety Population
16.2.5.3	Megestrol Acetate Accountability	Safety Population
16.2.6.1	Investigator Target Lesion Assessments by Visit	Full Analysis Set
16.2.6.2	Summary of Investigator Target Lesion Assessments and New Lesions by Visit	Full Analysis Set
16.2.6.3	Investigator Non-Target Lesion Assessments by Visit	Full Analysis Set
16.2.6.4	Best Overall Response	Full Analysis Set

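### Does the SAP's definition of an enrolled subject shut a dosed but ineligible woman out of the Safety Population and the deviation listing?

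*SAP*

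**What the plan says.** The opening paragraph of SAP Section 8 makes three linked statements:

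- On who counts as enrolled: "All subjects who sign the informed consent, satisfy all eligibility requirements and are assigned a subject number".
- On everyone else: "Subjects who do not satisfy the criteria as enrolled subjects are considered screen failures".
- On how the later analysis sets are nested: "The following subsets of the enrolled subjects will be used for all other analyses".

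Section 8.1 then defines the Safety Population as "all subjects who receive at least one full or partial dose of either study treatment", with no eligibility condition. Section 20 records this as a deliberate departure from Protocol 7.2.1, in a sentence that begins "This SAP updates this to the following definition: The Safety Population will consist of all subjects who receive at least one full or partial". The Full Analysis Set (8.2) is built on the Safety Population.

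Section 10.4 classes as major deviations "Any violations of the inclusion or exclusion criteria or subject compliance in study drug administration outside of the 80-120% acceptable range". The deviation listing (16.2.2) is assigned to All Enrolled Subjects. Protocol 8.1.6 names the entry of a subject who failed a criterion among the deviations that must be notified to the sponsor.

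**The concern.** Taken word for word, these sections do not fit together. A woman who received study drug and was later found to breach a criterion fails the Section 8 definition. She then becomes a screen failure and falls outside every set nested in the enrolled group. Sections 8.1 and 20 put her in the Safety Population because she was dosed. Her breach is what Section 10.4 wants listed, but listing 16.2.2 draws on a population from which the breach has removed her.

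The timing makes the point sharper. Section 7 has deviations identified and populations fixed before any analysis, so a breach found late would be known when the sets are drawn up. Nothing in Section 8 says that eligibility is taken as believed at entry.

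At stake is a consistent account of each treated woman. In an abbreviated report made almost wholly of listings, one subject could appear as never enrolled in one place and as treated in another. Six listings run on All Enrolled Subjects: 16.2.1.1, 16.2.1.3, 16.2.1.4, 16.2.1.5, 16.2.2 and 16.2.3.

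**Working it through.** No sample size, power or error rate is involved. The check is a comparison of passages, followed by simple counts.

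**What the eligibility clause does.** Protocol 3.3 and SAP 5.1 give a potential subject her identification number after consent and before screening procedures. Consent plus a number therefore cannot distinguish an enrolled subject from a screen failure; the eligibility clause has to do that. Three other places treat eligibility the same way, as the outcome of screening:

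- SAP 4.5 makes meeting the criteria the condition for being enrolled.
- SAP 5.1 enrols PrR-positive women who satisfy the criteria into Treatment Period 1.
- SAP 10.1 gives unmet eligibility criteria as a reason for screen failure.

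Nothing in Section 8 removes enrolled status from a woman whose breach is found later. Protocol 4.3 also restricts study drug to enrolled subjects, so under the plan's own procedure anyone dosed has already passed the gate.

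**The two readings compared for a dosed woman later found ineligible:**

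| Place | Eligibility judged at entry | Eligibility re-judged at lock |
|---|---|---|
| SAP 8 status | Enrolled | Screen failure |
| SAP 8.1 and 20 | In the Safety Population | In by 8.1 and 20, out by the nesting sentence |
| SAP 10.4, listing 16.2.2 | Listed as a major deviation | Omitted |
| Listing 16.2.1.2 (All Screened Subjects) | Not a screen failure | Shown, with the reason for failure (10.1) |
| AE, ECG and laboratory listings | Shown | Shown, since they name the Safety Population |

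The left-hand column has no conflict.

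**Could an enrolled subject have an eligibility violation even on the strict reading?** Yes. Inclusion criterion 15 applies only to Treatment Period 2, and eligibility is checked again at Visit 1 (Protocol 5.4.2). A woman properly enrolled in Treatment Period 1 could breach it later. Section 10.4 and listing 16.2.2 therefore have content on either reading.

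**Counts.** SAP 4.5 gives 36 screened and 25 enrolled. Taking the 25 as part of the 36:

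- Screen failures: 36 − 25 = 11, or 11/36 = 30.6%.
- One hypothetical dosed ineligible woman, counted among the 25: 1/25 = 4.0%. The strict reading would leave 24 enrolled and 12/36 = 33.3% screen failures.
- The same woman, if the 25 already leaves her out: 1/26 = 3.8%.

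No planned output calculates any of these percentages; disposition and screen failures are listed by subject (SAP 10.1).

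**What depends on the reading.** Disease control and response rates are not calculated (SAP 14.4, 14.5). No hypothesis test is planned (3.5). The Per Protocol Set is no longer applicable (8.3), and no PK samples were taken (3.3). The only table (QTc categories) and the only figure (swimmer's plot) run on the Safety Population.

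**The case for a change.** The strongest case for amending is that the entry-gate reading has to be inferred. Section 8 does not state it, the nesting sentence is explicit, and the plan plainly expects ineligible entrants, since Protocol 8.1.6 and SAP 10.4 both provide for them. Two or three sentences would settle the matter, and listing membership is most of what this abbreviated report delivers.

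What stands is that the wording is loose and that a strict reader could find the contradiction. The rest is weaker:

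- Section 8.1 and Section 20 settle the Safety Population by a specific rule stated twice. An analyst would not set that aside for a general lead-in.
- The Section 9.2 sentence "All data will be included in safety analysis" adds little support. It sits under missing data, straight after the statement that missing values are not estimated, and is not a rule about populations.
- Listing 16.2.1.5 is titled only "Inclusion and Exclusion" and may simply show each subject's status on the criteria.
- Redefining enrolled as entered into a period or dosed has a cost. If entry means starting treatment, an eligible woman who withdrew before her first dose would become a screen failure, and the reported 25 could change.

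**Conclusion.** No change is needed. The lead-in to Section 8 leaves out when eligibility is judged. The numbering procedure and SAP 4.5, 5.1 and 10.1 supply the sensible answer: at entry. A woman later found ineligible then stays enrolled, stays in the Safety Population if dosed, and is listed as a major deviation.

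The size is at most a matter of which listing carries a subject. Each such woman would be 4.0% of 25 or 3.8% of 26, and the documents do not say that there is one. Even on the strict reading her ineligibility would appear in listing 16.2.1.2, and her dosing and safety data in the Safety Population listings. No estimate, test or conclusion would move.

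This rests on two assumptions: that the analysts follow the specific dosing rule in 8.1 and 20, and that the 25 enrolled were counted as women who passed screening at the sites. If a dosed ineligible woman does come to light, a line in the clinical study report on how she was classed is enough.

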8.1 Safety Population

1. The Safety Population will consist of all subjects who receive at least one full or partial dose of either study treatment. For subjects treated solely in Treatment Period 1 this will include all subjects treated with at least one full or partial dose of MA. For all other subjects, the Safety Population will include all subjects treated with at least one full or partial dose of either MA or SC. Safety data will be reported separately for subjects in Treatment Period 1 who do not go on to Treatment Period 2, and for those subjects in Treatment Period 1 who are treated in both periods.

8.2 Full Analysis Set

The Full Analysis Set (FAS) will consist of all Safety Population subjects treated in Treatment Period 2 who either undergo a tumor assessment at Visit 4, Week 12 (i.e. they have not discontinued Treatment Period 2 prior to Visit 4, Week 12) or those who have discontinued Treatment Period 2 prior to Visit 4, Week 12 solely due to documented disease progression since Treatment Period 2 dosing started. This population will be used for efficacy evaluation.

